3 DETERMINATION OF SAMPLE SIZE

A sample size of 196 enrolled and randomized subjects randomized 1:1 to the investigational arm (Acoustic Enhancer with URS-LL) and the control arm (URS-LL) was selected based on consideration of the primary endpoint. Assuming no more than 10% non-evaluable subjects, this provides a randomized sample size 176 subjects (88 per arm).

The primary hypothesis test for the treatment success outcome is as follows:

 $H_0: p_{AE} \le p_{Control} \text{ vs } H_1: p_{AE} > p_{Control}$

Where p_{AE} is the acoustic enhanced response rate and $p_{Control}$ is the control response rate (no acoustic enhancement). Using a one-sided 0.025 Farrington-Manning test, a 55% response rate in the control arm, and a 75% response rate in the investigational arm, the sample size provides 80% power for the analysis. The 55% control arm response rate is based on reported results for laser lithotripsy with CT-based follow-up as described in the protocol, while the 75% response rate in the investigational arm is based on exploratory clinical studies.

4 STUDY ASSESSMENTS

All assessments related to primary and secondary endpoints are included in a separate analysis plan.

4.1 LASERING TIME AND INTERVENTIONAL STONE PROCEDURES

While the secondary endpoint, total radiant energy (TRE), is a more rigorous and broadly applicable indicator of improved stone erosion, pitting and fragmentation through the generation of additional stone-fragmenting shockwaves, a demonstration of lower mean lasering time in the Acoustic Enhancer arm compared to the standard laser arm could be clinically important. Total lasering time (seconds) will be summarized as a numeric variable during the Treatment/Procedure [Day 1].

Interventional stone procedure(s) on stone(s) that were treated as part of the AEROLITH study will be identified as basketing for retrieval of stone material and other as collected on the procedure CRF page. This will be summarized categorically.

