6.4. Additional Observations

- 6.4.1. Mean total lasering time. While total radiant energy is a more rigorous and broadly applicable indicator of improved stone erosion, pitting and fragmentation through the generation of additional stone-fragmenting shockwaves, a demonstration of lower mean lasering time in the Acoustic Enhancer arm compared to the standard laser arm could be clinically important.
- 6.4.2. Additional interventional stone procedure(s) on stone(s) that were treated as part of the AEROLITH study.
- 6.4.3. Adverse Events (AEs) by type over time, severity, seriousness, and relatedness. AEs will be tabulated and summarized as counts and percentages. AEs will also be cross tabulated according to:
 - Severity
 - Unanticipated Adverse Device Effect (UADE)
 - Seriousness (Serious Adverse Event (SAE), Non-serious AE)
 - Device-Relatedness (Unrelated, Possibly Related, Probably Related, Definitely Related)
 - Procedure-Relatedness (Unrelated, Possibly Related, Probably Related, Definitely Related)

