- If possible, perform retrograde stone displacement into the pelvis/calyx following institution standard protocol.

During laser lithotripsy, small volumes of Acoustic Enhancer are placed in the urine near the stone at periodic intervals (refer to the IFU).

Lasering is continued until any visible remaining fragments are estimated to be 1-2 mm in size or smaller.

For the purposes of this study, no basketing will be performed for stone retrieval. If basketing is performed, this will be captured and recorded as a major protocol deviation. No other concomitant procedures, including diagnostic procedures, are allowed during the treatment. Any concomitant procedure (i.e., basketing) being conducted will be documented as a major protocol deviation.

Post-treatment, ureteral stents will be placed in all subjects for 3 to 14 days. If a stent cannot be placed, this will be captured and recorded as a minor protocol deviation.

Investigators must record any stents remaining >14 days post procedure and document any observations of calcification or encrustation. If a stent is removed outside of the window (3-14 days), this will be captured and recorded as a minor protocol deviation. If calcification and/or encrustation is observed, an Adverse Event CRF should be completed.

Document any adverse events observed during the procedure (see Adverse Events section below).

8.3. Recovery and Discharge

Recovery and discharge procedures will follow standard protocol at the treating institution. Any adverse events will be documented.

8.4. Follow up call at Day 14 (14 days +/- 4 days after each procedure)

- Conduct a follow-up call after the treatment.
- Document any reported AEs since last observation was performed (see Adverse Events section below).
- If symptoms of Urinary Tract Infection (UTI) are reported by subjects, conduct a urinalysis and subsequent urine culture if clinically indicated to verify presence/absence of UTI.
- Document all prescription medications. In addition, document any non-prescription medication that may impact stone disease, acting as stone formation promoters (e.g., calcium or ascorbic acid) or stone formation inhibitors (e.g., magnesium or citric acid).
- Record date of stent removal in the 14-day Follow Up Evaluation CRF

Note: If a stent is removed at >14 days but <30 or <90 days post procedure, please complete Follow Up (On-site) Evaluation CRF and select unscheduled visit for visit type.

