10.8. Additional Observations

Mean total lasering time will be analyzed as a numeric endpoint using the ITT Population. A two- sided t-test with equal variance assumed will be used to evaluate the null hypothesis that mean time is similar in both groups. A 95% two-sided CI for the mean difference will be provided. An ANOVA will be used to evaluate mean total laser time as a function of location, treatment, and location x treatment interaction. Least square means will be provided with ANOVA p-values.

The number and percentage of subjects receiving subsequent additional interventional stone procedures for stone(s) that were treated in the AEROLITH study will be summarized. A Likelihood-Ratio chi-square test will be used to evaluate the null hypothesis that the proportion of subjects with at least one secondary stone treatment is equal in both groups. In addition, the total number of secondary stone treatments will be summarized and a Cochran- Armitage trend test will be used to evaluate the null hypothesis that there is no trend in the number of stones between the groups.

Use and quantity of prescription pain medication for managing stone-associated pain will be characterized by timing and type of medication and will be summarized descriptively for the ITT and PP Population.

Residual stone size will be summarized descriptively as a continuous variable and rate of absence of residual stones as a categorical variable. These will be summarized for the ITT and PP Populations.

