- An Adverse Device Effect (ADE) is any untoward and unintended response to a medical device, including events arising from insufficient or inadequate instructions for the employment of the device or its use.
- A Serious Adverse Event (SAE) is any AE that:
 - results in death;
 - is life threatening;
 - results in or prolongs hospitalization;
 - results in permanent impairment of a body function or permanent damage to a body structure;
 - necessitates medical or surgical intervention to preclude permanent impairment of a body function or permanent damage to a body structure;

Note: For the purposes of this protocol, for a subject who has been treated with standard URS-LL or with Acoustic Enhancer with URS-LL and requires an additional treatment to further fragment or eliminate the stone, this additional procedure will not be considered an adverse event.

- Led to fetal distress, fetal death, or a congenital abnormality or birth defect;
- Other serious medically important event.

Note: Planned hospitalization for a pre-existing condition, or a procedure required by the CIP, without serious deterioration in health, is not considered a serious adverse event

• An Unanticipated Adverse Device Effects (UADE):

The investigational device exemption (IDE) regulations and ISO 14155:2020 (Clinical Investigation of medical devices for human subjects – Good clinical practice) defines an unanticipated adverse device effect (UADE) as any *serious* adverse effect on health or safety, any life-threatening problem or death caused by, or associated with a device, if that effect, problem, or death was not previously identified in nature, severity, or degree of incidence in the clinical investigational plan or risk analysis; or any other unanticipated serious problem associated with a device that relates to the rights, safety, or welfare of subjects" (21 CFR Part 812.3(s)). UADEs must be reported by the clinical investigator to the sponsor and the reviewing IRB, as described below:

- Investigators are required to submit a report of a UADE to the sponsor and the reviewing IRB as soon as possible, but in no event later than 10 working days after the investigator first learns of the event (21 CFR Part 812.150(a)(1)).

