8.1.3 Exploratory Efficacy Endpoint(s)

- Mean total lasering time (sec). Lasering time is captured in minutes and seconds but will be converted entirely to seconds for analysis.
- Difference in means of total lasering time between groups
- Number of subjects receiving subsequent additional interventional stone procedures (URS-LL, SWL)) for stone(s) that were treated in the AEROLITH study
- Number and percentage of subjects receiving subsequent additional interventional stone procedures for stone(s)
- Number of secondary stone treatments
- Number of subjects taking prescription pain medication for managing stoneassociated pain prior to treatment, post treatment, at Day 14 and at Day 30(defined as a medication categorized as a Pain Medication and answered "Yes" to "Medication taken for Kidney Stones?")

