13 CHANGES TO THE ANALYSES PLANNED IN THE PROTOCOL

In the protocol it is stated that the total number of secondary stone treatments will be summarized and a Cochran-Armitage trend test will be used to evaluate the null hypothesis that there is no trend in the number of stones between the groups. This was removed from the SAP. Because subjects exit the study 30 days after receiving treatment, this data is unlikely to be available.

No further changes exist between the protocol-defined statistical analyses and those presented in this statistical plan.

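### SAP 4.1 identifies interventional stone procedures as basketing 'and other' on the procedure CRF page, contradicting the subsequent-procedure endpoint in Protocol 6.4.2 and 10.8 and SAP 8.1.3 and 8.2.4

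*SAP*

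**What the plan says.** The protocol lists, among its additional observations (6.4.2), "Additional interventional stone procedure(s) on stone(s) that were treated as part of the AEROLITH study". Section 10.8 turns this into an analysis variable: "The number and percentage of subjects receiving subsequent additional interventional stone procedures for stone(s) that were treated in the AEROLITH study will be summarized".

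The SAP describes the variable in three places:

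- **SAP 4.1** repeats the subject of Protocol 6.4.2 without the word 'additional'. It says these procedures "will be identified as basketing for retrieval of stone material and other as collected on the procedure CRF page" and are to be summarized as a categorical item.
- **SAP 8.1.3** lists the number of subjects with "subsequent additional interventional stone procedures (URS-LL, SWL)) for stone(s" treated in the trial.
- **SAP 8.2.4** compares the arms in the ITT population with a likelihood-ratio chi-square test, two-sided at 0.05. The tested variable, STREAT, is a yes/no flag for additional treatment. The output is Table 14.2.2, whose title contains neither 'additional' nor 'subsequent'.

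On basketing, Protocol 8.2 says "For the purposes of this study, no basketing will be performed for stone retrieval", and "If basketing is performed, this will be captured and recorded as a major protocol deviation". On re-treatment, Protocol 11.1 says that where a treated subject "requires an additional treatment to further fragment or eliminate the stone, this additional procedure will not be considered an adverse event".

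**The concern.** The endpoint asks whether a patient needed another procedure on the same stone after the study treatment. SAP 4.1 points instead to an act by the operator during the study treatment. The two differ in timing and in meaning. Basketing takes fragments out, whereas re-treatment suggests that fragments were left behind.

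If the flag were built from 4.1, a subject who was basketed and never treated again would count as re-treated. A subject re-treated before exit could be missed. Equal basketing in both arms would dilute a real difference. Unequal basketing would bias the comparison, and the operator is not among those blinded under Protocol 7.4. Excluding major deviations from the per-protocol population gives no protection, because Table 14.2.2 is an ITT table.

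Fewer later stone events is part of the benefit rationale in Protocol 9.2, so a reader may give this table some weight although it is exploratory.

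**Working it through.** The documents state no re-treatment rate, basketing rate or power for this comparison, so there is no figure to reproduce. The check is a comparison of the definitions.

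| Source | What is counted | When | Data source named |
|---|---|---|---|
| Protocol 6.4.2 | Additional procedures on treated stones | Not stated | None |
| Protocol 10.8 | Subsequent additional procedures | After study treatment | None |
| SAP 4.1 | Basketing 'and other' | Apparently Day 1 | Procedure CRF page |
| SAP 8.1.3 | Subsequent additional procedures, URS-LL and SWL named | After study treatment | None |
| SAP 8.2.4 (STREAT) | Subsequent procedures; yes/no flag | After study treatment, with no date rule | None |

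1. **Can 4.1 and 8.1.3 describe the same variable?** No. Index-procedure basketing is neither subsequent nor an instance of URS-LL or SWL re-treatment. Protocol 8.2 classifies it as a deviation of the index procedure.
2. **Is the procedure CRF page the Day 1 page?** Probably. The preceding paragraph of 4.1 places lasering time at the Day 1 treatment visit. The CRFs are not among the documents, so this remains an inference.
3. **Which source would a programmer use?** Only 4.1 names one. The order of its heading, lasering time then interventional stone procedures, matches Tables 14.2.1 and 14.2.2. The list of procedure details in SAP 7 does not include basketing.
4. **Does another planned analysis recover later re-treatment?** Not the adverse-event tables, because of the Protocol 11.1 note. The visit instructions in Protocol 8.4 to 8.6 and the Schedule of Events list no item for further stone procedures. Protocol 8.4 does mention an on-site follow-up form with an unscheduled-visit option, which could carry the information.
5. **Is the difference a declared change?** No. SAP 13 drops only the total-count summary and its trend test, then says that no further changes exist.
6. **Could the separate analysis plan settle it?** SAP 4, 5 and 8 assign the primary and secondary endpoints to that plan. This endpoint is exploratory and belongs to this SAP.

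**The case against.** The best defence is that the sections governing the comparison state the right concept. SAP 8.1.3 and 8.2.4 both refer to subsequent procedures, and 8.1.3 names URS-LL and SWL. SAP 4.1 specifies no test and includes 'and other', so basketing is not its whole definition. On this view 4.1 is loose wording that the endpoint section overrides. That stands to this extent: a reader might infer that the trial plans to compare basketing instead of re-treatment, and the documents do not support that. They show an unresolved contradiction.

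Three other strong readings also fail:

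- **That later procedures are certain to be missed.** The CRFs are not available. Protocol 8.4 and 8.6 use wording that allows for more than one procedure. Protocol 12.2 provides for unscheduled-visit data and requires records of any interventions. The source is unnamed; non-capture is not shown.
- **That SAP 13 concedes the data will be missing.** Its words are "Because subjects exit the study 30 days after receiving treatment, this data is unlikely to be available", given as the reason for dropping the count and trend analysis. Keeping a yes/no comparison over the available follow-up is not in itself inconsistent.
- **That the table would reverse the direction of effect.** This needs basketing to differ by arm, for which the documents give no evidence.

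The contradiction survives all of this, because the only source the SAP names is the wrong one and nothing says that 8.1.3 takes precedence.

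**Conclusion.** The contradiction is real and should be corrected before the flag is programmed. SAP 4.1 states a rule that conflicts with Protocol 6.4.2 and 10.8 and with SAP 8.1.3 and 8.2.4. If followed, it would count a disallowed intra-operative act as re-treatment and could leave out later re-treatments.

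The reach is one exploratory comparison, Table 14.2.2. It lies outside the sequential testing in Protocol 10.5 and is not needed for study success under Protocol 6.6. No primary, secondary or primary safety result changes. The size of any distortion cannot be estimated from the documents, since neither basketing nor re-treatment rates are given.

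The conclusion that 4.1 conflicts with the endpoint rests on the text alone. The consequence that later procedures could be missed also assumes that the page in 4.1 is the Day 1 page and that no other form is used to build STREAT.

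**What to change.** - In SAP 4.1, delete the definition based on basketing and the procedure CRF page.
- In SAP 4.1 and for STREAT in 8.2.4, define the variable as any stone procedure on a study-treated stone performed after the end of the index procedure and up to study exit. Name the follow-up and unscheduled-visit forms as the source, and confirm against the CRFs that these forms record the procedure and its date.
- Report index-procedure basketing separately, under procedure details (SAP 7) or protocol deviations (SAP 6.5).
- State with Table 14.2.2 that the comparison covers only procedures performed before exit, which is about 30 days for most subjects. Add 'subsequent' to the table title.

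The cost is SAP wording and a check of the existing forms; no test or sample size changes. An exit-form field for planned re-treatment is optional. It would add an investigator-judged item that the protocol does not define, and it is not needed to resolve the contradiction.

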5 GENERAL ANALYSIS AND REPORTING CONSIDERATIONS

The primary efficacy analysis will be included in a separate analysis plan and is not covered in this SAP.

P-values for the analysis covered by this SAP will be rounded to three decimal places. If a p-value is less than 0.001 it will be reported as "< 0.001." If a p-value is greater than 0.999 it

will be reported as "> 0.999." Where reported, all confidence intervals will be two-sided 95% confidence intervals (CIs).

Continuous data will be summarized using descriptive statistics: n, mean, standard deviation, median, minimum and maximum, unless otherwise noted.

Categorical variables will be summarized using frequency counts and percentages. When count data are presented, the percentage for zero counts will be suppressed in order to draw attention to the non-zero counts. The denominator for all percentages will be the number of subjects in that treatment group within the population of interest, unless otherwise noted.

The following conventions will be used throughout the study analysis:

- Day 0 is the date of the procedure.
- Baseline value is defined as the last measurement prior to the procedure.
- Change from baseline is defined as post-baseline value minus baseline value.
- Duration of an AE will be computed in days, calculated by using stop date minus the start date if AE occurs on or after the procedure. If reported as ongoing at the time of database lock, the duration will be calculated using the date of the last visit or the last date of any AE for the subject in the database, whichever is later. Missing dates will be imputed as described in Table 2.
- The number of days in the study is computed as: [Date of study completion or withdrawal minus the date of procedure].
- If duplicate values are obtained at a given visit (e.g., repeated vital sign measurements), the last value will be used unless it is noted that the measurement was in error for that value. Values that compromise interpretation will not be used in summaries (e.g., values that were obtained post-procedure will not be summarized as pre-procedure values).

5.1 ADJUSTMENTS FOR COVARIATES

5.2 NO ADJUSTMENTS FOR COVARIATES ARE PLANNED.HANDLING OF MISSING DATA

No imputation or adjustment for missing assessment data will be used.

See the following table for imputation rules for partial to fully missing or medication dates.

Missing Start Date Portion	Prior to Treatment	Same as Treatment Start Date	After Treatment Start Date
Day	Month and Year < Month and Year of first treatment:	Month and Year = Month and Year of first treatment:	Month and Year > Month and Year of First Treatment:
	Start Day = 1	Start Day = Day of	Start Day = 1
	Stop Day = last day of the month	first treatment Stop Day= last day of the month	Stop Day= last day of the month
Day and Month Define Day as above, then:	Year < Year of first treatment:	Year = Year of first treatment:	Year > Year of first treatment:
	Start Month = Jan	Start Month =	Month = Jan
	Stop Month = Dec	Month of first treatment	Stop Month = Dec
		Stop Month = Dec	
Day, Month, and Year	To be conservative, con date of first treatment, c date of last contact.	npletely missing start ompletely missing en	dates will be set to the dates will be set to the

Table 2:	Table of Imputation	Rules for Missing	Medication Dates

After following these imputation rules, if the start date is imputed as a date after the end date, the start date will be set to the end date to provide a positive duration for the event incidence.

Applaud's medical monitor will assess missing AE study medication relationship or severity which will be used analysis purposes.

No other imputation is planned for safety data.

5.3 **ASSESSMENT TIME WINDOWING**

No visit windows will be utilized in this study and all safety and efficacy assessment summaries will be based on the nominal protocol-specified assessment times. Thus, if the protocol specified Day 30 visit occurs on study Day 31, it will still be summarized as a "D30" assessment.

5.4 POOLING OF INVESTIGATOR SITES

No pooling is planned for this study.

5.5 ADJUSTMENTS FOR MULTIPLICITY

The study will include a single primary effectiveness endpoint to be tested at the one-sided 0.025 level. If that hypothesis is met, two other endpoints will be considered sequentially. If the first secondary hypothesis is statistically significant, the second hypothesis will also be assessed. Hence, the overall Type I error for the study is controlled for the specified hypotheses.

5.6 **EXAMINATION OF SUBGROUPS**

No subgroup analysis is planned.

6 SUBJECT SUMMARIES

6.1 ANALYSIS POPULATIONS

6.1.1 Intent-to-Treat (ITT) Population

The ITT population consists of all randomized subjects who meet the study inclusion/exclusion criteria. Subjects who develop UTI or having their stone move to the middle/distal ureter between the time they were screened and were found to be eligible at the time they were randomized, or who no longer meet any of the other inclusion/exclusion criteria at the time of the procedure, will not be treated under the protocol. These subjects will not be included in the ITT analysis. The ITT population will be used for all effectiveness analyses with groups based on the randomized treatment.

